4.9.1 Variables

Safety and tolerability data encompass vital signs, skin evaluations, ECGs, laboratory values, number and severity of adverse events, instruments to assess depression and suicidality such as electronic Columbia-Suicide Severity Rating Scale (eC-SSRS) and Personal Health Questionnaire Depression Scale (PHQ-8).

4.9.2 Descriptive Analyses

4.9.2.1 Vital Signs

All vital signs data (systolic and diastolic Blood Pressure (BP), Heart Rate (HR), weight) will be listed up to Week 52 by treatment group, subject, and visit/time and when reference ranges are available, abnormalities will be flagged. Summary statistics for absolute values and change from baseline, will be provided by treatment group and visit/time. The number and percentage of subjects within each baseline category (low, normal, high and missing) versus the post-baseline category (low, normal, high and missing) of vital signs will also be summarized at all post-baseline visits (the low, normal and high categories will be defined as follows for these parameters: heart rate: <60 beats/min, 60-100 beats/min, >100 beats/min, systolic blood pressure: <90 mmHg, 90-139 mmHg, >139 mmHg, diastolic blood pressure: <60 mmHg, 60-89 mmHg, >89 mmHg and temperature: <36.5°C, 36.5-37.3°C, >37.3°C).

4.9.2.2 Skin Evaluations

All skin evaluation data including any findings not typical of psoriasis, conduction of further skin assessments such as biopsy will be listed by treatment group, subject and visit up to Week 52.

4.9.2.3 ECG Evaluations

The ECG evaluations will be reported by treatment group for the induction period and the overall study. The number and proportions of subjects with a normal, abnormal, abnormal clinically significant or unevaluable overall 12-lead ECG evaluation will be reported by treatment group. In addition, summary statistics for the absolute values and change from baseline for ECG parameters will be provided by treatment group and visit/time. ECG parameters comprise HR, PR interval, QRS, QT interval and the corrected QT intervals i.e. QTcB using Bazett's correction and QTcF using Fridericia's correction QTcB is calculated by dividing the QT interval by the square root of the preceding R-R interval while QTcF is calculated by dividing the QT interval by the cube root of the preceding R-R interval.

A shift analysis from baseline will be implemented for PR, QRS, QT, QTcB and QTcF intervals and HR describing the change from baseline (normal, abnormal) to end of period/study (normal, abnormal, abnormal clinically significant or unevaluable) in ECG parameters.

The number and proportion of subjects with abnormal elevated QT, QTcB and QTcF intervals i.e. exceeding the upper limit value of 450 ms, 480 ms and 500 ms will be summarized by treatment group. The number and proportion of subjects who experience an increase from baseline in QT, QTcB and QTcF interval greater than 30 ms and 60 ms will also be reported by treatment group.

All ECG data will be listed by treatment, subject and visit/time up to Week 48, abnormalities will be flagged.

4.9.2.4 Clinical Laboratory Evaluations

All laboratory data up to Week 52 including serology tests (at screening only), pregnancy tests (women only) and urinalyses will be listed by treatment, subject, and visit/time. If reference normal ranges are available, laboratory abnormalities will be flagged and the CTCAE grade included.

Summary statistics of hematology, chemistry and urinalysis data and their change from baseline in SI units will be provided by treatment group and visit/time. Unscheduled measurements e.g. laboratory re-test due to abnormal laboratory results or unplanned visits due to safety concerns will be excluded from this analysis.

In addition, the number and percentage of subjects with abnormal, high or low, hematology, chemistry and urinalysis values will be summarized by treatment group.

Individual subject changes from baseline to worst post-baseline assessment in laboratory parameters graded using CTCAE will be summarized using shift tables by treatment group for the induction and overall period. The worst post-baseline laboratory assessment will correspond to the worst post-baseline CTCAE grade observed on-treatment over all visits (including scheduled and unscheduled measurements).

For non-graded laboratory parameters, shift tables will present the number and percentages of subjects within each baseline category (low, normal, high and missing) versus the post-baseline category (low, normal, high and missing). The categories will be defined by using the minimum and maximum values. Minimum/maximum baseline value will be the lowest/highest non-missing value observed during the baseline period i.e. before the first dose of study treatment. The minimum/maximum post-baseline laboratory assessment will be determined relative to the reference normal ranges i.e. to on-treatment lowest decrease and highest increase from minimum/maximum baseline over all visits (including scheduled and unscheduled measurements) for the considered period. In addition, a shift table from normal/high baseline category to low post-baseline category will be produced using the minimum value. Similarly, a shift table from low/normal baseline category to high post-baseline category will be produced using the maximum value.

Scatterplots of minimum/maximum absolute laboratory values during baseline vs. minimum/maximum absolute laboratory values during the treatment period will be presented with lines indicating the reference limits (Lower Limit Normal, Upper Limit Normal and absence of change from baseline).

4.9.2.5 Adverse Events

Treatment-Emergent AEs (TEAEs) per treatment period are AEs that emerge while on study treatment during a given treatment period (e.g. induction period), having been absent pre-treatment, or that worsen during the considered period (e.g. induction period) relative to the pre-treatment state i.e. after baseline and on or prior to the date of the last visit of the considered period (e.g. Week 12 for the induction period). On study treatment during a treatment period is defined as the period from the first study treatment administration at the start of period (e.g. Week 0 for the induction period) up to the last visit of the treatment period for subjects who did not discontinue treatment during the considered period (e.g. Week 12 for the induction period) or for subjects who discontinued during the considered period, up to the end of the considered period or up to 8 weeks after the last dose of study treatment, whichever occurs first. TEAEs will be assigned to the actual treatment period to which they are considered treatment-emergent.

When considering the study overall, treatment-Emergent AEs (TEAEs) are AEs that emerge while on study treatment i.e. from the first study treatment administration up to 8 weeks after the last dose of study treatment, having been absent pre-treatment, or that worsen during study treatment relative to the pre-treatment state i.e. after baseline.

If the classification of an AE cannot be clearly established because of missing or incomplete date/time of AE, the AE will be classified as treatment-emergent. No imputation of missing or partial AE start and end dates will be performed.

To determine whether an AE is pre-treatment, on-treatment or post-treatment in case of partial or missing AE dates, the rules below will be followed:

- If the start date is incomplete and either the end date is incomplete or available:
 - if the non-missing part of the start date infers that the AE occurred post-treatment, the AE will be considered as post-treatment.
 - If the partial or complete end date indicates that the AE occurred prior to the first dose of study drug, the AE will be considered as pre-treatment.
 - If the partial start date does not give any evidence as to when the AE occurred during the study, and the end date infers that the AE stopped after the first dose of study drug, the AE will be flagged as on-treatment for all periods for which the first dose of study drug was started before the end of the AE.
 - If the partial or complete start and end dates do not indicate as to when the AE started and ended compared to the first dose of study drug of any period, the AE will be flagged on-treatment for all periods.
- If both start and end dates are both missing: the AE will be considered on-treatment and therefore a TEAE for all periods.

To determine the worsening of an AE during study treatment, the maximum severity for each AE during the baseline period will be considered. In case of missing severity, the conservative approach below will be followed:

- If an AE has a missing severity during the study treatment, it will be defined as treatment-emergent.

- If the severity of an AE is missing at baseline and this event continues during the study treatment, this AE will be considered as treatment-emergent.

Adverse events of Special Interest (AESI) include cytopenias, liver function test changes/enzyme elevations, infections, injection-site reactions, allergic/hypersensitivity reactions, cerebrocardiovascular events, malignancies, depression, Crohn's disease and ulcerative colitis. Additional adverse events may be identified as being of special interest during the study and prior to first unblinding.

An overview table will present the number and percentage of subjects experiencing these types of AEs below by treatment:

- TEAEs,
- TEAEs by relationship to investigational product,
- serious TEAEs including deaths,
- TEAEs by maximum severity,
- deaths,
- and TEAEs leading to study treatment discontinuation.

This table will be produced for all separate treatment periods and the overall periods (refer to Table 4.3, Table 4.13, Table 4.14 and Table 4.15).

For the overall period, the exposure-adjusted incidence per 100 subject-years will also be presented. The exposure-adjusted incidence will be calculated by dividing the number of subjects with AEs by the total person years of exposure during the treatment period (refer to Section 4.7). This result will be multiplied by 100 to obtain the exposure-adjusted incidence per 100 subject-years.

The AESI will also be displayed with an overview table by treatment for each treatment period and the overall periods.

The incidence of subjects with TEAEs will be summarized by the Medical Dictionary for Regulatory Activities (MedDRA) System Organ class (SOC) and Preferred Term (PT) and by treatment group. A subject with multiple AEs in the same SOC (or with the same PT) will only be counted once for that SOC (or PT). The PTs will be presented in decreasing order of frequency over all treatment groups within the SOC. Similarly, incidence tables will be produced for treatment-related TEAEs, for serious TEAEs, for TEAEs by maximum severity, for TEAEs leading to deaths and study drug discontinuations. In addition, the number and percentage of subjects with AESI will be presented by treatment group classed by SOC and PT. An additional summary table will be created to include the relatively common TEAEs i.e. with an incidence greater than 5%. All information obtained on adverse events will be listed by treatment group and subject. A listing of deaths will be also provided by indicating the study period in which the deaths occurred in the enrolled population.

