Study drug will be administered via subcutaneous injection. All doses are comprised of two injections, each of 1mL, which should be administered at least 5 centimetres apart on any quadrant of the abdomen or the upper thigh. The body location for injections should not be repeated at consecutive study visits. Injections should not be given in areas where the skin is

tender, bruised, erythematous, or indurated. Areas of the skin affected by psoriasis should be avoided as injection sites.

For subjects assigned to M1095 or placebo, the site approved unblinded administrator will be instructed to inject the subject with 1ml of solution from vial A and 1ml of solution from vial B. Subjects assigned to secukinumab will be dosed with 2 x 150mg/mL pre-filled syringes, as directed. Blinded study personnel should not be in attendance while study drug is being prepared or administered. Used syringes should be placed immediately out of sight in a sealed sharps container.

Subjects should be observed for approximately 2 hours after the first dose of study drug and 1 hour for subsequent doses. At Week 12 all subjects should be observed for approximately 2 hours. If a subject experiences symptoms indicative of an acute hypersensitivity reaction after an injection, this should be discussed with the Medical Monitor before the next study visit/injection.

Regulatory agencies require accounting for the disposition of all study drugs received by each clinical site. The investigator is responsible for maintaining information related to drug disposition which at minimum consists of the date received, date dispensed, quantity dispensed and the subject to whom the drug was dispensed.

At the end of the study, the investigator should return unused study drug and packaging to the sponsor's representative. Local destruction may be permitted with the sponsor's approval.

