## 6.6 Dose Modification

### 6.6.1 Week 12

Subjects randomized to placebo will receive M1095 120mg at Week 12, 14, 16 and then q4w.

Subjects randomized to M1095 30mg or 60mg and who do not achieve an IGA score of 0 or 1 at Week 12 will be dose escalated to receive M1095 120mg q4w.

Site personnel will enter the IGA score into the IRT prior to the study drug kit being assigned at Week 12.

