### 8.1.7 Weeks 12, 24, 36, 48

There is a visit window of  $\pm 2$  days for Weeks 12 and 24, and  $\pm 5$  days for Weeks 36 and 48.

Fasting blood samples should be obtained, so the visit should be conducted in the morning and the subject should not have had breakfast.

Patient reported outcomes (PRO) i.e. DLQI, EQ-PSO, SF-36, PHQ-8, and eC-SSRS should be performed before any other study procedures, assessments or consultations.

IGA, BSA and PASI should be conducted after the PROs and before other tests, procedures and consultations.

Study drug should be administered **after** completion of all other study procedures.

The following assessments will be performed and information collected:-

- DLQI
- EQ-PSO
- SF-36
- PHQ-8
- eC-SSRS
- IGA
- BSA
- PASI
- AEs
- Concomitant Medications
- Skin Evaluation
- Physical Examination
- Vital Signs
- Laboratory Analysis Chemistry and Haematology (Fasting, Central Laboratory)
- Urinalysis (Local)
- Urine Pregnancy Test (Local) – if positive, study drug must be withheld and a Serum Pregnancy Test (Central Laboratory) performed
- ECG (Standard 12 Lead, Central ECG Laboratory)

- Blood Sample for Immunogenicity (must be pre-dose)
- Blood Sample for Pharmacokinetics (must be pre-dose)
- Study Treatment (allocated via IRT) with the exception of Week 48
- At Week 24, the investigator should carefully consider the subject's response and if there has been a worsening of psoriasis compared to baseline then the investigator should consider discontinuing the subject from the study if they are not receiving adequate benefit from their participation.

### 8.1.8 Week 14

There is a visit window of  $\pm 2$  days for the Week 14 visit.

IGA, BSA and PASI should be performed before any other study procedures, assessments or consultations.

Study drug should be administered **after** completion of all other study procedures.

The following assessments will be performed and information collected:-

- IGA
- BSA
- PASI
- AEs
- Concomitant Medications
- Skin Evaluation
- Vital Signs
- Laboratory Analysis Chemistry and Haematology (Central Laboratory)
- Study Treatment (allocated via IRT)

### 8.1.9 Week 16, 20, 28, 32, 40

There is a visit window of  $\pm 2$  days for Weeks 16 and 20, and  $\pm 5$  days for Weeks 28, 32 and 40.

Patient reported outcomes (PRO) i.e. PHQ-8, and eC-SSRS should be performed before any other study procedures, assessments or consultations.

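### SAP 4.9.2.5 lets a reaction to the placebo arm's first M1095 injection, given on the Week 12 visit date, count as a placebo event in the Week 0–12 safety tables

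*SAP*

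**What the plan says.** SAP 4.9.2.5 defines a treatment-emergent event per period as one that emerges on treatment, or worsens, after baseline and "on or prior to the date of the last visit of the considered period (e.g. Week 12 for the induction period". It defines being on treatment within a period as running "from the first study treatment administration at the start of period (e.g. Week 0 for the induction period", and "up to the last visit of the treatment period for subjects who did not discontinue treatment during the considered period". Assignment is covered by one sentence: "TEAEs will be assigned to the actual treatment period to which they are considered treatment-emergent". The date rules that follow deal only with missing or partial dates.

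On the dosing side, Protocol 6.6.1 states: "Subjects randomized to placebo will receive M1095 120mg at Week 12, 14, 16 and then q4w". The same section says that subjects on 30 mg or 60 mg "who do not achieve an IGA score of 0 or 1 at Week 12 will be dose escalated to receive M1095 120mg q4w". The visit procedures, including those for Week 12 in Protocol 8.1.7, put the injection last: "Study drug should be administered after completion of all other study procedures". Protocol 6.2 adds: "At Week 12 all subjects should be observed for approximately 2 hours".

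SAP Table 4.2 labels each subject in the induction safety tables by the treatment received most during induction. SAP Table 4.3 shows the Plac/120mg group from Week 12 onwards in the overall tables and includes it in Total M1095.

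**The concern.** Weeks 0 to 12 are the only period with a placebo control. The window that feeds those tables closes on a calendar date, and on that date Arm 1 changes from placebo to active drug. Injection-site reactions and allergic or hypersensitivity reactions are both named as events of special interest, and they are the events most likely to start on the day of an injection.

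If such a reaction in Arm 1 is counted in induction, an active-drug event sits in the control column. In Arm 1 the error can only raise the placebo rate. The same tables (treatment-emergent events, serious events and events of special interest up to Week 12) are listed for the first interim analysis in SAP Table 2.1 and reviewed by the DMC.

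**Working it through.** The plan states no figure for this point, so there is none to reproduce. The check has two parts: following the rules for one event, and sizing the effect under stated assumptions.

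**Following one event.** Take an Arm 1 subject who gets the Week 12 injection and develops a reaction during the observation period.

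| Question | Rule | Result |
|---|---|---|
| Is onset within the induction window? | SAP 4.9.2.5: inclusive of the Week 12 visit date | Yes |
| Which induction column? | SAP Table 4.2: treatment received most in induction | Placebo |
| Does it also meet the next window? | SAP 4.9.2.5: opens at the first administration of the period, which is this injection | Yes |
| Does any rule choose between the two? | The assignment sentence refers back to the same definitions; the date rules cover only incomplete dates | No |
| Where else does it appear? | SAP Table 4.3: from Week 12 onwards | Plac/120mg and Total M1095 |

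Arm 1 is not among the groups in Table 4.14 (maintenance/escalation safety). Its double attribution is therefore between the induction table and the overall tables, not between two period tables. A reaction that starts the next day is outside the induction window and is unaffected.

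**Size in the placebo column.** The arm size is about 50 (Protocol 4.1). One subject is 1/50 = 2 percentage points. The documents give no same-day reaction rate, so p is assumed. Expected extra placebo subjects = 50p, and the chance of at least one is 1 − (1 − p)^50. This treats all 50 as dosed at Week 12 and none as already having such an event.

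| p | Expected extra, 50p | Chance of at least one |
|---|---|---|
| 2% | 1.0 | 64% |
| 3% | 1.5 | 78% |
| 5% | 2.5 | 92% |
| 10% | 5.0 | 99% |

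**Net effect on the difference.** The M1095 arms are also injected on the Week 12 date, so the same rule adds subjects to their columns. Assume a constant, independent same-day rate p per M1095 injection and no background events. An M1095 arm with k earlier doses gains only subjects with no earlier reaction, p(1 − p)^k. Placebo gains p. Net narrowing = p − p(1 − p)^k, with k = 4 for Arms 2–4 (Weeks 0, 2, 4, 8) and k = 6 for Arm 5 (Weeks 0, 2, 4, 6, 8, 10).

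| p | Placebo gain (points) | Arms 2–4 gain | Net, Arms 2–4 | Arm 5 gain | Net, Arm 5 |
|---|---|---|---|---|---|
| 2% | 2.0 | 1.84 | 0.16 | 1.77 | 0.23 |
| 3% | 3.0 | 2.66 | 0.34 | 2.50 | 0.50 |
| 5% | 5.0 | 4.07 | 0.93 | 3.68 | 1.32 |
| 10% | 10.0 | 6.56 | 3.44 | 5.31 | 4.69 |

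At p = 10%, for Arms 2–4, a window closed before the Week 12 dose gives 1 − 0.9^4 = 34.4% against 0%. The current window gives 1 − 0.9^5 = 41.0% against 10.0%. The difference falls from 34.4 to 31.0 points.

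If reactions occur almost only at a subject's first M1095 dose, the M1095 arms gain almost nothing at Week 12 and the net narrowing approaches p itself, 2 to 10 points over this range.

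**Escalators.** With the planned IGA 0/1 rate above 88% (Protocol 9.2), at most about 12% × 50 = 6 subjects per low-dose arm receive a first 120 mg injection at Week 12. Their same-day reactions are labelled 30 mg or 60 mg in induction. At p = 10% that is 6 × 0.10 = 0.6 subject, or 1.2 points.

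**The case against.** The strongest objection concerns size. A reader might infer that the whole placebo gain of 2 to 10 points is the loss of contrast. The documents do not support that: every M1095 arm is dosed at Week 12 too, and under a constant per-injection rate most of the placebo gain is matched. This stands.

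A reader might also infer that the rule hides M1095 risk. It does not remove the event from M1095: it remains under Plac/120mg and Total M1095 in the overall tables, under Total 120 mg in the pooled table (SAP Table 4.13), and in the subject listings. The DMC sees unblinded data and holds two unblinded safety meetings before the first interim analysis. This stands as well.

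On the wording, the phrase about the date of the last visit could be read as attached only to events that worsen. New events would then be governed by the on-treatment definition, which runs up to the last visit. That does not settle the matter, because the injection is part of that visit and no pre-dose limit is given. Elsewhere the SAP does use the dose as a boundary: the design section for Week 24 (1.4), the later-period and overall baseline for the placebo arm (4.1), and later-period concomitant therapy (4.8). None of these governs adverse events.

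Week 24 is not a comparable problem. No group starts a new active drug or a higher dose there, so it is only a point of consistency. Finally, the phase 1 figure of 1 in 33 is a discontinuation for an injection-site reaction in subjects who received three doses. It is not a same-day rate and cannot anchor p.

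**Conclusion.** The point holds. Followed literally, SAP 4.9.2.5 places a same-day reaction to Arm 1's first M1095 injection in the Placebo column of the Week 0–12 tables, and nothing else in the plan corrects this. The event is attributed twice, not lost.

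Each affected subject adds 2 points to a 50-subject placebo column. The net narrowing of the M1095–placebo difference is about 0.2 to 3.4 points for Arms 2–4, and up to 4.7 for Arm 5, at constant per-injection rates of 2 to 10%. It is larger only if reactions cluster at the first dose. These rates are assumptions, as are independence between injections, no background events and no Arm 1 dropout before Week 12.

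No formal safety comparison is planned (SAP 4.9), so no test is affected. The reason to act is that the misattribution in Arm 1 has a known direction, falls in the only placebo-controlled safety tables, and is cheap to remove. The escalator effect is a smaller dose-label issue.

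**What to change.** In SAP 4.9.2.5, end each period's window immediately before the first dose of the next period, and keep the visit date as the end only for subjects not dosed at that visit. Assign a same-day onset with no recorded time to the later period, unless the record shows that it began before the injection. Use the same boundary in Tables 4.3 and 4.13, and at Week 24 for consistency.

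The cost is a short change of wording and one programming rule; trial conduct does not change. The SAP already uses dose date and time for exposure (4.7.1). It mentions the time of an adverse event only in connection with missing or incomplete data, so the documents do not show whether onset time is collected, and the default may carry much of the weight. The downside is that a few untimed events that began before the Week 12 injection would move to the M1095 period. List the reassigned events so that the effect can be seen.
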